4.1.3 Dropouts, Missing/Incomplete Data, and Outliers

Missing data occurs when any requested data is not provided, leading to blank fields on the collection instrument. These data will be indicated using a “blank” in participant listing displays. Answers such as “Not applicable” and “Not evaluable” are not considered to be missing data and should be displayed as such. In general, missing data will not be imputed unless specifically stated in this SAP.

The missing/incomplete dates for adverse events, and prior/concomitant medications, procedures (for the purpose of computing durations and treatment emergent status of adverse events, medications and procedures status (prior and/or concomitant)), ALS symptom onset date and diagnosis date will be imputed according to the rules specified in Appendix 2. Partial dates will still be displayed in listings.

Uncoded events at the time of analysis will be assigned the string “UNCODED” as the system organ class, and the reported term will be used as the preferred term so they can be included in the summary tables. In the final dataset, all the adverse events should be coded.

Uncoded medications at the time of analysis will be assigned the string “UNCODED” as the Anatomical-Therapeutic-Chemical (ATC) summary level(s) and the verbatim term will be used as the preferred name, so they can be included in the summary tables. In the final dataset, all the medications will be coded.

4.2 Historical Controls

Due to the nature of this EAP study, there is no treatment-naive randomized control group. To estimate the treatment effect, historical controls are introduced to compare with Trehalose treated participants. The historical controls will be constructed through the propensity score (PS) matching and PS based stratification approaches, respectively.

4.2.1 Eligible Historical Control Analysis Set

The eligible historical control analysis set will be constructed from the available databases relating to clinical outcomes in ALS consisting of previous ALS clinical research study participants who:

- met major eligibility criteria from this EAP study if related information was collected in historical database, including:
 - Inclusion criteria 2: Age 18 years or older.
 - Exclusion criteria 2: Screening glucose ≥ 140 mg/dl
 - Exclusion criteria 6: Screening body weight > 144 kilograms
- and had known mortality information
- and had baseline and at least one post-baseline ALSFRS-R total scores recorded
- and/or had baseline and at least one post-baseline measurements of Vital Capacity (VC) including the collected SVC or Forced Vital Capability (FVC)

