4.1 Inclusion Criteria

1. Sporadic or familial ALS.
2. Age 18 years or older.
3. Cohort 1: Patients do not qualify for any reasonably accessible ongoing clinical trial.
4. Cohort 2: Patients have completed Regimen E RCT and the open label extension (OLE) period of the HEALEY ALS Platform Trial, or completed Regimen E RCT of the HEALEY ALS Platform Trial if the OLE is not available at the site, and are not eligible for enrollment in another treatment regimen of the platform study.
5. Capable of providing informed consent and complying with study procedures, in the Site Investigator's (SI's) opinion.
6. Participants have established care with a physician at a specialized ALS center involved in the study and will maintain this clinical care throughout the duration of the EAP.
7. Participants must have a life expectancy of at least 6 months in SI's opinion (applicable for Cohort 1 only).

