3. ANALYSIS SETS

3.1 Definition of Analysis Sets

The following analysis sets are defined for this study:

Analysis Set	Definition
Screened Set	All participants who signed the informed consent form.
Full Analysis Set (FAS)	All participants who received at least one dose of Trehalose.
Per-Protocol Set (PPS)	
All participants included in FAS and who satisfy all the criteria below:
 
 - Did not have a major protocol deviation that affected the scientific integrity of the trial. - Received at least 85% and not more than 125% of the prescribed infusion volume up to the point of drug withdrawal/ last infusion. Data after drug withdrawal/ last infusion will not be included. 
The PPS will be finalized prior to the database closure.

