4.1.1 Definitions, Derivations and Classifications

Definition of Baseline

The baseline value for all endpoints (i.e., laboratory parameters and vital signs) will be the last available value prior to the first dose of study treatment in Trehalose group, and the date of first study visit in historical control group.

Assessments taken on the same day as study treatment will be assumed to be before study treatment unless indicated to be obtained post-study treatment.

Definition of Day 1

Study Day 1 is defined as the first day of study treatment in Trehalose group, and the date of first study visit in historical control group. This will also be considered the reference start date.

Definition of Study Day

Study Day will be computed as follows:

- Study Day = (Date of event – Date of study day 1) + 1 if the date of the event is on or after the date of study day 1.
- Study Day = (Date of event – Date of study day 1) if the date of the event is prior to the date of the study day 1.

Derivations Involving Dates

The number of days between two dates, the date of interest and the reference date, will be calculated as (Date of event – Reference date) + 1 when the event date is on or after the reference date; or, as (Reference date – Date of event) + 1 when the event date is before the reference date. The resulting value is then converted to years, months, or weeks, as appropriate. Partial dates will be imputed before calculating the number of days (See Appendix 2 for partial or unknown date imputation rules).

Common Calculations

Change from baseline (CHG) will be calculated as:

$$\text{Change from baseline} = \text{Actual (observed) value at post baseline visit} - \text{baseline value}$$

Percent change from baseline (PCHG) will be calculated as:

$$\text{Percent change from baseline (\%)} = 100 * (\text{Change from baseline at post baseline visit} / \text{Baseline value})$$

If baseline is not available, the change from baseline and percent change from baseline will not be calculated and will remain missing.

Demographics

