4.7.1 Overall Survival

4.7.1.1 Definition of Endpoint

The overall survival (OS) will be calculated in months, defined as the time from the date of first study treatment administration to the date of death due to any cause. Participants not known to have died at the time of the analysis will be censored on the date they were last known to be alive.

OS time (months) = (date of event/censored - date of first study treatment administration + 1) / 30.4375.

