4.7.1.2 Main Analytical Approach

OS will be summarized for both EAP study treatment groups and historical control groups based on the FAS.

The number and percentage of participants with event or censored will be presented by treatment group. The Kaplan-Meier estimates of the quartiles of the survival distribution along with corresponding 95% confidence intervals will be calculated. The survival rate (%) and 95% CI will be displayed for 2 months, 4 months, 6 months, 7 months, and 8 months.

To assess the differences in OS between PS matched (based on the pre-specified caliper width for main analysis) Trehalose group and historical control group: the hazard ratio (HR) and corresponding 95% confidence interval will be estimated using the Cox proportional-hazards model, stratified by PS matched ID. The two-sided log-rank test stratified by PS matched ID will be performed for generation of the two-sided p-value, which will be considered statistically significant if $p < 0.05$. The Kaplan-Meier plot for Trehalose and historical control groups will be presented.

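### Treated participants and historical controls enter the overall survival comparison under different survival conditions, so the hazard ratio can be biased in either direction and no planned sensitivity analysis tests this

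*SAP*

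**What the plan says.** **Treated side.** Protocol 4.1, item 7 reads: "Participants must have a life expectancy of at least 6 months in SI's opinion (applicable for Cohort 1 only". Cohort 2 has no such screen. The Full Analysis Set (SAP 3.1) is "All participants who received at least one dose of Trehalose", so no later assessment is needed.

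**Control side.** SAP 4.2.1 takes people who "met major eligibility criteria from this EAP study if related information was collected in historical database, including" age, glucose and weight. It also asks for known mortality, "and had baseline and at least one post-baseline ALSFRS-R total scores recorded", "and/or had baseline and at least one post-baseline measurements of Vital Capacity (VC"). Day 1 and baseline for controls are "the date of first study visit in historical control group" (SAP 4.1.1).

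**Adjustment.** SAP 4.2.2 names nine propensity score covariates, among them age, BMI, bulbar onset, ALSFRS-R total, pre-baseline slope and % predicted VC. None records the investigator's prognosis. More covariates may be added.

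**Analysis.** SAP 4.7.1.2 fits a Cox model and a log-rank test stratified by matched pair and calls p < 0.05 statistically significant. Of the Kaplan-Meier display it says: "The survival rate (%) and 95% CI will be displayed for 2 months, 4 months, 6 months, 7 months, and 8 months". The HR has no such limit: those not known to have died "will be censored on the date they were last known to be alive" (SAP 4.7.1.1), and protocol 6.6.10 adds a second vital-status check at about the last patient's last visit (LPLV). SAP 4.7.1.3 and 4.7.1.4 vary the caliper, the use of PS strata, the PAV composite and the Per-Protocol Set.

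**The concern.** Each group passes a survival filter that the other does not.

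- Cohort 1 is selected on a forecast of the outcome itself. If that forecast carries information beyond the matched covariates, early deaths are thinned on the trehalose side only and the HR falls.
- Controls must be alive and assessed at a later visit, yet that waiting time counts as follow-up. Early deaths are thinned on the control side only and the HR rises.

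Every planned variant keeps the same entry rules and the same time zero. Agreement among them would therefore look like robustness without testing either filter. Survival is first in the efficacy order of protocol Section 9.0, and SAP Section 1 leaves open use of the results in a regulatory submission. An HR away from 1, in either direction, could be read as a drug effect or as harm.

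**Working it through.** The plan gives no power, event count or effect size for survival, so there is no survival figure to reproduce. Its only power statement concerns NfL and has no bearing here.

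**1. Inputs.**
- From the documents: half of people with ALS die within 3 years of symptom onset (protocol 1.1).
- Assumed: that median, 36 months, applied from study entry with a constant hazard.
- Assumed: s, the share of those who would die within 6 months whom the screen removes beyond what the propensity score captures.
- Assumed: v, the time in months of the first required control visit.
- Assumed: no drug effect, equal group sizes, and no pair stratification.

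**2. Baseline mortality.** λ = ln(2)/36 = 0.01925 per month. With F(t) = 1 − exp(−λt), 6-month mortality is m = F(6) = 10.9% and 8-month mortality is F(8) = 14.3%.

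**3. Each filter.**
- Screened Cohort 1 mortality is (1 − s)F(t)/(1 − sm) up to 6 months and [F(t) − sm]/(1 − sm) after. For s = 25% at 8 months: (0.1428 − 0.0273)/0.9727 = 11.9%, against 14.3% unscreened. The ratio of cumulative hazards, ln(1 − 0.119)/ln(1 − 0.143), is about 0.82.
- Control survival is 1 up to v and exp(−λ(t − v)) after. At 8 months the cumulative-hazard ratio is 8/7 = 1.14 for v = 1 and 8/5 = 1.60 for v = 3.

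**4. Large-sample Cox HR.** This is the θ that solves Σ[d₁ − (d₁ + d₀)θS₁/(θS₁ + S₀)] = 0, where d and S are deaths and survival in each group. Follow-up to 8 months, all Cohort 1:

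| s | v = 0 | v = 1 | v = 3 |
|---|---|---|---|
| 0 | 1.00 | 1.15 | 1.64 |
| 10% | 0.93 | 1.07 | 1.52 |
| 25% | 0.82 | 0.94 | 1.34 |
| 50% | 0.63 | 0.73 | 1.03 |

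The column v = 0 is the screen alone, and the row s = 0 is the control rule alone.

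**5. What moves it.**
- With half the treated group in Cohort 1, the screen alone gives 0.96, 0.91 and 0.81 for s = 10%, 25% and 50%.
- Longer follow-up weakens both filters. At 12 months, s = 50% with v = 0 gives 0.75, and s = 0 with v = 3 gives 1.37.
- An 18-month median changes little: s = 50% with v = 0 gives 0.64 at 8 months.

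**6. False-positive rate.** 3000 simulated unstratified log-rank tests, 70 against 70, 8 months, all Cohort 1, 36-month median. The chance of p < 0.05 favouring trehalose (nominal 2.5%) is 5.9% at s = 25% and 14.4% at s = 50% for the screen alone. It is 3.4% and 9.1% with v = 1, and 2.3% with v = 3 and s = 50%. For the control rule alone at v = 1, the chance of p < 0.05 against trehalose is 5.4%.

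**7. Landmarks in the same model.** Taking Day 90 as month 3 and following to month 8, the HR is the same for v = 0, 1 and 3: 0.94, 0.85, 0.82 and 0.70 for s = 10%, 25%, 30% and 50%. The control rule is gone, but the screen still acts in months 3 to 6. From a 6-month landmark the HR is 1.00 for every s and v shown.

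**The case against.** A reader might infer that the plan is tilted towards trehalose: Cohort 1 is screened on survival, controls are not, and the comparison covers 2 to 8 months. The documents do not support that.

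- SAP 4.2.1 puts its own survival condition on controls, acting the other way. Since s, v and the cohort split are not given, the net sign cannot be fixed.
- The 2-to-8-month times are display points. The HR uses all follow-up, which dilutes both effects.
- Pre-baseline slope, BMI, VC, ALSFRS-R and age cover much of what an investigator would weigh, and both the criteria list and the covariate list are open.
- Cohort 2 is unscreened and pooled with Cohort 1.
- Cohort 1 consists of people who do not qualify for accessible trials (item 3), which may select for worse prognosis.
- The size of the screen effect is driven by s, which is assumed. The survival figure in the protocol runs from symptom onset, not from entry.

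The plan is also open about its limits. SAP Section 2 calls the comparisons exploratory, SAP 4.2.3 says matching is conditional on the included covariates, and SAP 4.2.4 assumes no unobserved confounders.

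All of this stands against a one-directional claim. It does not remove the mismatch. Two unmeasured biases of opposite sign cannot be relied on to cancel, and a general caveat about unmeasured confounding does not test two specific filters that are written into the entry rules.

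**Conclusion.** The mismatch in entry conditions is in the text; its net direction is not known. In the illustration, the null HR to 8 months runs from 0.73 to 1.52 with both filters acting (s = 10% to 50%, first required control visit at 1 to 3 months, all Cohort 1, constant hazard with a 36-month median). The screen alone gives 0.93 to 0.63 and the control rule alone 1.15 to 1.64. These are ranges over assumptions, not estimates of the bias in this study. A larger Cohort 2 share shrinks the downward part only. The survival HR should not be interpreted, for or against trehalose, without analyses that address both filters. Because the comparison is exploratory, this is a change the SAP should make; it does not invalidate the study.

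**What to change.** Add to SAP 4.7.1.3:

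1. **Landmark comparisons of overall survival**, with the clock restarted in both groups and only people alive and under follow-up at the landmark. Use Day 90, which removes the control post-baseline condition if the first required visit falls by then. Use also 6 months, with vital-status follow-up to LPLV, which clears the window of the life-expectancy screen as well.
2. **HRs by period** (0–3, 3–6 and after 6 months) and **separately for Cohort 1 and Cohort 2**.
3. **A bias table** giving the s that would explain the observed HR, over a stated range of v.
4. **A statement on interpretation:** a Day-90 landmark HR below 1 does not exclude entry selection and must be read with the 6-month landmark and the bias table.

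The cost is programming on data already planned for collection, plus a few sentences. The price is precision. At the illustrative hazard, 70 people yield 70 × 0.1428 = 10.0 deaths in months 0–8, 70 × (0.9439 − 0.8572) = 6.1 in months 3–8 and 70 × (0.8909 − 0.8572) = 2.4 in months 6–8. The 6-month landmark therefore depends on follow-up beyond month 8. Intervals will be wide, so these remain sensitivity analyses.

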4.2.3 PS Matching

PS matching method (Rosenbaum and Rubin, 1985) matches Trehalose participants with eligible historical control participants based on PS such that matched Trehalose participants and placebo participants are comparable in terms of covariates used in PS determination. This process mimics randomization to create two comparable groups with a caution of limitation that the matching is conditional on included covariates.

PS matching will be conducted in a 1:1 ratio using a more optimal caliper width based on the standard deviation of the logit of the propensity score [22]. The constructed historical control group will be used for the main analysis on the exploratory efficacy endpoints defined in Section 4.7. In addition, the propensity score matching will be performed with other different caliper widths if available to construct additional matched historical control groups for sensitivity analysis of the related exploratory efficacy endpoints.

Participants who are not selected in the matching process will be excluded from further analysis. Following matching, baseline covariates will be summarized for participants in PS matched Trehalose group and PS matched historical control group to check if the balance is generally achieved.

The PS matched identifier (ID) will be included as stratification factor to estimate the overall treatment effect and difference between the PS matched Trehalose group with historical control group in the analysis of exploratory efficacy endpoints defined in Section 4.7.

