4.2.4 PS Stratification

The participants from Trehalose group and the eligible historical control analysis set will be sequentially stratified into appropriate strata according to the PS quintiles of the Trehalose treated participants. This allows each stratum to contain roughly an equal number of Trehalose treated participants. The strata that do not contain both Trehalose and historical control participants will be dropped from the matched samples. As participants in each stratum have similar propensity scores, each stratum can be conceptualized as a quasi-RCT, and the observed covariates will be better balanced between the two groups under the assumption that there are no unobserved confounders and the PS model has been correctly specified.

The overlap of PS distributions between the two groups within each stratum will be assessed. The covariate balance between the two groups after the PS stratification will be checked.

The PS stratification-built strata will be included as stratification factor to estimate the overall treatment effect and difference between the PS stratification-based Trehalose group and historical control group in the analysis of exploratory efficacy endpoints defined in Section 4.7.

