4.3 Participant Disposition

A summary of participant disposition will be provided for Screened Set by treatment cohort and overall for the following categories. The number and percentage of participants will be presented.

- Participants screened (signed the informed consent form)
- Screen failures with reasons for failure

- Participants treated
- Participants with major protocol deviation
- Participants completed study or discontinued from study with discontinuation reasons
- Participants completed treatment or discontinued from treatment with discontinuation reasons

The study duration (weeks), defined as (date of study completion/discontinuation – date of informed consent signed + 1) / 7, will be summarized descriptively by treatment cohorts and overall.

The participant disposition for FAS and the participants who failed screening with reasons (if any) will be listed.

Protocol deviations for FAS will be provided in a listing including the deviation type and deviation description for major and minor deviations, respectively.

The number and percentage of participants included and excluded from the analysis sets FAS and PPS will be tabulated overall and for each treatment cohort. Reason(s) for exclusion from each set will be summarized overall and by reason for exclusion. The ALSFRS-R and SVC evaluable participants who have baseline and at least one post-baseline assessment of ALSFRS-R or SVC will be summarized under both FAS and PPS. The participants excluded from analysis sets and exclusion reasons will be listed for all Screened Set.

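### The historical control set for overall survival requires a post-baseline functional measurement, so controls who died before it are excluded while trehalose deaths count from the first dose

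*SAP*

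**What the plan says.** SAP 4.2.1 builds a single eligible historical control set. After the carried-over eligibility criteria and known mortality, a control must meet the condition "and had baseline and at least one post-baseline ALSFRS-R total scores recorded", and/or have the matching pair of VC measurements.

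Time zero is set in SAP 4.1.1. Day 1 is the "first day of study treatment in Trehalose group, and the date of first study visit in historical control group".

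On the trehalose side, SAP 3.1 defines the FAS as "All participants who received at least one dose of Trehalose". OS (SAP 4.7.1.1) runs from first dose to death from any cause, and anyone not known to have died "will be censored on the date they were last known to be alive". SAP 4.3 recognises the parallel follow-up condition for trehalose, where "evaluable participants who have baseline and at least one post-baseline assessment of ALSFRS-R or SVC will be summarized under both FAS and PPS". That is a tabulation only and does not restrict OS.

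The pool is used twice. For matching (SAP 4.2.3): "The constructed historical control group will be used for the main analysis on the exploratory efficacy endpoints defined in Section 4.7". For stratification (SAP 4.2.4): "The participants from Trehalose group and the eligible historical control analysis set will be sequentially stratified into appropriate strata". In the main OS analysis (SAP 4.7.1.2) the HR and its interval "will be estimated using the Cox proportional-hazards model, stratified by PS matched ID".

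**The concern.** The two groups enter the OS comparison under different rules. A control needs at least one post-baseline functional measurement, but the control's survival time is counted from a visit before that measurement. The interval between the two is death-free by construction. No such interval exists for trehalose. This is immortal time in one arm only.

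The planned analyses cannot remove or reveal it. The propensity score in SAP 4.2.2 uses baseline covariates, while the selection is on what happened after baseline. Other calipers, PS strata and the PPS all keep the same control rule. No landmark, delayed entry or separate OS control set is specified. The OS (including PAV) comparisons in SAP 4.7.1.4 inherit the problem through their death component.

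SAP 2 makes the analyses descriptive and the p-values exploratory. Even so, SAP 4.7.1.2 calls p < 0.05 on this comparison statistically significant, SAP 4.2 introduces the controls to estimate a treatment effect, and SAP 1 says the results might enter a regulatory submission.

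**Working it through.** The documents give no OS event count, power or assumed HR, so there is no plan figure to reproduce. The calculation below illustrates the size of this one component.

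**Inputs**
- True HR = 1, taken as trehalose over control (the SAP does not state the orientation).
- Constant hazard L = ln2/36 = 0.01925 per month in both groups, from the statement in Protocol 1.1 and SAP 1 that half of people with ALS die within three years.
- 70 matched pairs, the planned enrolment. This is a ceiling, because unmatched participants are dropped.
- m = time to the control's first qualifying measurement: 1, 2 or 3 months. **Assumed**; the documents do not give it.
- T = follow-up: 6 months (about the 24-week treatment period), 8 months (the last survival time displayed in SAP 4.7.1.2), and 12 and 18 months (assumed; Protocol 6.6.10 allows later vital-status checks).

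**Formula.** In a Cox model stratified by 1:1 pair, only the first death in a pair is informative, and the HR estimate is the ratio of trehalose-first to control-first pairs.

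- P(trehalose first) = (1 − e^(−Lm)) + e^(−Lm) × ½(1 − e^(−2L(T−m)))
- P(control first) = e^(−Lm) × ½(1 − e^(−2L(T−m)))
- HR = 1 + (1 − e^(−Lm)) / [e^(−Lm) × ½(1 − e^(−2L(T−m)))]

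Example, m = 2 and T = 8: 1 + 0.03778 / (0.96222 × 0.10315) = 1.38.

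**Expected HR when the true HR is 1**

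| Follow-up T | m = 1 | m = 2 | m = 3 |
|---|---|---|---|
| 6 months | 1.22 | 1.55 | 2.09 |
| 8 months | 1.16 | 1.38 | 1.68 |
| 12 months | 1.11 | 1.25 | 1.41 |
| 18 months | 1.08 | 1.17 | 1.27 |

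At twice the hazard: 1.25, 1.60, 2.19 at 6 months and 1.14, 1.30, 1.49 at 12 months. A simulation of 20,000 trials of 70 pairs agrees with the 6-, 8- and 12-month rows to within 0.01.

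**Control deaths removed.** The share is (1 − e^(−Lm)) / (1 − e^(−LT)): 17%, 35%, 51% of those by 6 months, and 13%, 26%, 39% of those by 8 months.

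**Other models and inputs.** A separate large-sample simulation assumed 6-month mortality of 5–20% and m of 0.7–3 months. At 8 months the HR was 1.10–1.75 pair-stratified and 1.09–1.67 unstratified (the fallback in SAP 4.7.1.4). The shift was upward in all 24 scenarios. The PS-stratified model was not run.

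**Size against noise.** SE(log HR) = √(1/d_trehalose + 1/d_control), using expected first-in-pair deaths.
- 6 months: 7.35/6.01, 7.45/4.81, 7.53/3.60 deaths. SE 0.55, 0.59, 0.64. Shift 0.4, 0.7, 1.2 SE.
- 8 months: 9.45/8.11, 9.59/6.95, 9.71/5.79 deaths. SE 0.48, 0.50, 0.53. Shift 0.3, 0.6, 1.0 SE.

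**What would cancel it.** Give trehalose a hazard kL and solve for HR = 1:

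(1 − e^(−kLm)) + e^(−kLm) × k/(1+k) × (1 − e^(−(1+k)L(T−m))) = e^(−kLm) × 1/(1+k) × (1 − e^(−(1+k)L(T−m)))

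For m = 1, 2, 3 the required reductions in trehalose hazard are 18%, 35%, 51% (6 months); 14%, 27%, 40% (8 months); and 10%, 19%, 28% (12 months).

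**After correction.** With a common landmark at m, or with controls at risk only from their first qualifying measurement, the simulated HR returns to 0.99–1.01.

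**The case against.** The best counter-argument is that the follow-up conditions were meant per endpoint: ALSFRS-R follow-up for ALSFRS-R, VC follow-up for VC, and mortality information for OS. The list in SAP 4.2.1 does line up with the three compared endpoints. But the SAP never says so. It names one set and sends that set into both matching and stratification. If the endpoint-specific reading was intended, it needs to be written down.

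Several cautions about size stand. The visit interval is assumed, and it drives the result. The three-year figure runs from symptom onset, not study entry, and the same source statement puts deaths within five years at 90%, against 1 − e^(−60L) = 69% under this constant hazard. Seventy pairs is a maximum; with an illustrative 40, the 6-month shifts fall to 0.3, 0.6 and 0.9 SE. At 12 months with 70 pairs they are 0.3, 0.5 and 0.8 SE.

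The direction, taken alone, is against trehalose, so this rule by itself does not create a false benefit. Opposing selection is plausible. Protocol 4.1 requires a life expectancy of at least six months in Cohort 1 and completion of the parent trial in Cohort 2, and neither is among the criteria SAP 4.2.1 lists for controls. The known-mortality filter, and the loss of early control dropouts without a measurement, have unknown effects. All of this leaves the net sign open. It does not justify keeping an avoidable bias that the confidence interval will not reflect.

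**Conclusion.** The concern holds. As written, control time from the first study visit to the first recorded post-baseline ALSFRS-R or VC is death-free by construction, trehalose time is not, and every OS comparison is affected. With equal true hazards this component alone gives an HR above 1: about 1.1 to 1.7 over 8 to 12 months and 1.2 to 2.1 over 6 months, for a first control measurement at 1 to 3 months. These sizes rest on the assumed visit interval and hazard; the upward direction of this component does not depend on their exact values. The net direction of bias in the OS comparison is undetermined. Because OS is exploratory, this is something that should be fixed rather than a fatal flaw.

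**What to change.** For OS and OS (including PAV), adopt one of the following:

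1. **Separate OS control set.** Use the listed eligibility criteria, the baseline PS covariates, and a death or last-known-alive date, with no post-baseline ALSFRS-R or VC condition. Re-run PS estimation, matching and stratification on it.
2. **Common landmark.** Require both groups to be event-free at a fixed time, start the clock there, and require the control's qualifying measurement on or before it.
3. **Delayed entry.** Keep the present set, matches and strata, but count each control at risk only from the first qualifying measurement. State which measurement that is under the and/or wording.

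The present rule can stay for the ALSFRS-R and VC models. Under any option, report how many controls and control deaths the rule excludes, and state that the net direction of the remaining bias is undetermined. If an endpoint-specific reading was intended, say so in SAP 4.2.1 and define the OS set accordingly.

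**Cost.** The SAP is final at version 2.0, so this needs an amendment or a labelled additional analysis. Option 1 repeats the PS work for all calipers, strata, PPS and balance tables, and some matched controls will add nothing to the functional models. The documents do not show that the database holds vital status for people without follow-up visits; such controls would be censored near Day 1 and add little. Option 2 discards early deaths in both groups. Option 3 is the lightest, but in the pair-stratified model trehalose deaths before the matched control's entry contribute nothing.
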